4.3. WITHDRAWAL CRITERIA

Subjects will be free to withdraw from the study at any time without affecting their future medical care. Subjects who are withdrawn from active treatment will remain in the study for assessment of outcome relating to QoL measures.

The safety of the child is paramount in this study. Thus, children who experience anaphylaxis to an OIT dose at home, but who do not receive IM adrenaline as per the management plan, will have further updosing suspended until the family undergo retraining on the recognition and management of allergic symptoms.

A participant will be withdrawn from the study under the following circumstances:

- If, in the opinion of the study team, compliance with study procedures is suboptimal such that it compromises the patient's safety.
- If, in the opinion of the study team, further participation would adversely affect the participant's health.
- A child develops an exclusion criteria during the updosing phase of the study e.g. a new medication (which would normally be a contra-indication) is commenced.
- If consent is withdrawn or the subject fails to return for a study visit.
 In the event of a serious adverse reaction to OIT and/or if presenting with anaphylaxis requiring more than one IM adrenaline dose within 2 hours after an OIT dose.

Any subject excluded from further participation will not be replaced.

⁹ Sporik R, Hill DJ, Hosking CS. Specificity of allergen skin testing in predicting positive open food challenges to milk, egg and peanut in children. Clin Exp Allergy 2000; 30:1540–6.; AND Sampson HA. Utility of food-specific IgE concentrations in predicting symptomatic food allergy. J Allergy Clin Immunol 2001;107: 891–6.

¹⁰Papadopoulos NG, Arakawa H, Carlsen KH, et al. International consensus on (ICON) pediatric asthma. Allergy. 2012;67:976-97.

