5.2.4 MANAGEMENT OF SYMPTOMS DURING PEANUT EXPOSURE

Any allergic reaction happening during the observation period following dose administration will be managed according to the British Society for Allergy and Clinical Immunology (BSACI) Allergy Action Plans for children (Figure 6).

[figure not shown]
Mild-moderate (non-anaphylactic) symptoms (as defined in Figure 6) will be treated with cetirizine as per local policy. Symptoms of anaphylaxis will be treated initially with IM adrenaline. Where feasible, the child or parent will use their adrenaline auto-injector device to administer the (first) dose of adrenaline in this event, as this can increase compliance with the Plan's recommendations outside the home environment and reduce anxiety relating to the use of auto-injector devices.

Allergy Action Plan

Clinic details

THIS CHILD HAS THE FOLLOWING ALLERGIES:

How to give EpiPen®

Form fist around EpiPen® and PULL OFF BLUE SAFETY CAP

SWING AND PUSH ORANGE TIP against outer thigh (with or without clothing) until a click is heard

HOLD FIRMLY in place for 10 second

REMOVE EpiPen®. Massage injection site for 10 seconds

Keep your EpiPen device(s) at room temperature, do not refrigerate.

For more information and to register for a free reminder alert service, go to www.epipen.co.uk

Patient support groups:

http://www.allergyuk.org or www.anaphylaxis.org.uk ©The British Society for Allergy & Clinical Immunology www.bsaci.org

Mild-moderate allergic reaction:

- · Swollen lips, face or eyes
- Itchy / tingling mouth
- Abdominal pain or vomiting
- Hives or itchy skin rash
- Sudden change in behaviour

ACTION:

- · Stay with the child, call for help if necessary
- · Give antihistamine:
- · Contact parent/carer

(if vomited, can repeat dose)

Watch for signs of ANAPHYLAXIS (life-threatening allergic reaction):

AIRWAY: Persistent cough, hoarse voice,

difficulty swallowing, swollen tongue

Breathing: Difficult or noisy breathing,

wheeze or persistent cough

Consciousness: Persistent dizziness / Pale or floppy

Suddenly sleepy, collapse, unconscious

If ANY ONE of these signs are present:

- 1. Lie child flat. If breathing is difficult, allow to sit
- 2. Give EpiPen® or EpiPen® Junior
- 3. Dial 999 for an ambulance* and say ANAPHYLAXIS ("ANA-FIL-AX-IS")

If in doubt, give EpiPen®

After giving Epipen:

- 1. Stay with child, contact parent/carer
- 2. Commence CPR if there are no signs of life

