5.3.4.3 CHANGES TO THE PROTOCOL DUE TO REACTIONS

In the event of an allergic reaction to a dose of OIT within 2 hours of a dose, either at updosing in hospital or after a dose given at home, the following measures will be taken:

- For a single reaction consisting of wheeze, persistent cough, difficulty breathing, stridor or marked swallowing difficulties, the family must not give further OIT doses without contacting the research team. The previous lower dose will be given the next possible day, ideally under medical observation on the Research Unit.
- For skin symptoms, itchy mouth, rhinoconjunctivitis or mild abdominal symptoms, reassurance to families will be provided and the current dose will be continued, with daily contact with the study team as needed.
- For persistent reactions for 5-7 days (within 2 hours of the OIT dose) consisting of abdominal pain, rhinoconjunctivitis or skin symptoms, the dose will be reduced to the previous dose.
- In the event of other symptoms that prove difficult to the child, the dose can be reduced at investigator's discretion.

Where a dose reduction is required, the subsequent dose increase will be performed at least 2 weeks later at the Research Unit in hospital under supervision.

In the event of omitted doses:

- If a single dose of OIT is missed, the subject can continue with the usual dose.
- If 2 4 days of OIT are missed, give the previous dose until the subject can attend the research unit for the next updosing.
- If more than 4 days are missed, daily doses should stop and the subject must attend the research unit.

In the event of an intercurrent illness, where symptoms occur but are not related temporally to dose administration, families should contact the research team to discuss reducing the dose depending on symptoms type and intensity.

 $^{^{\#}}$ Dose to be given as 4 whole peanuts + peanut flour to make a total dose of 3 gram peanut protein

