6. ADVERSE EVENT REPORTING

6.1 DEFINITIONS

An adverse event is any occurrence or worsening of an undesirable or unintended sign, symptom, laboratory finding, or disease that occurs during participation, including occurrences that are not necessarily caused by or related to a study intervention. An adverse event will be followed until it resolves or until 30 days after a participant terminates from the study, whichever comes first.

A **serious adverse event** (SAE) is defined as any adverse event that suggests a significant hazard. This includes but is not limited to any of the following:

- 1. Death: Any death that occurs during the study must be reported whether considered treatment related or not.
- 2. A life-threatening event: Any adverse therapy experience that, in the view of the investigator, places the participant at immediate risk of death from the reaction as it occurred.
- 3. Inpatient hospitalization or prolongation of existing hospitalization.
- 4. Persistent or significant disability.
- 5. An event that requires intervention to prevent permanent impairment or damage. An important medical event that may not result in death, be life threatening, or require hospitalization may be considered an SAE when, based on appropriate medical judgment, it may jeopardize the participant and may require medical or surgical intervention to prevent one of the outcomes listed above.
- 6. Important AEs that are not immediately life-threatening or do not result in death or hospitalization but may jeopardise the subject or may require intervention to prevent one of the other outcomes listed in the definition above, should also be considered serious.

The adverse event can be described as 'expected' if it caused symptoms and/or signs that could be reasonably described as a consequence of an allergic reaction to peanut exposure within the protocol. Symptoms of an allergic reaction are defined as any described within this protocol.

An adverse event is considered "unexpected" when its nature or severity is not consistent with the investigator's protocol.

An adverse event is defined as "**related**" when it has resulted from the administration of any of the research procedures. Related adverse events are defined as "**adverse reactions**".

Any symptoms requiring treatment for anaphylaxis (adrenaline, steroids, salbutamol) following an OIT dose will be classified as a SERIOUS ADVERSE REACTION.

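### An OIT reaction treated with one adrenaline dose leads to withdrawal under sections 4.3 and 6.1 but to continued dosing under section 5.3.4.3, and nothing ranks the two rules

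*Combined protocol and SAP*

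**What the plan says.** **Withdrawal.** Section 4.3 opens its list with "A participant will be withdrawn from the study under the following circumstances". The item at issue is "In the event of a serious adverse reaction to OIT and/or if presenting with anaphylaxis requiring more than one IM adrenaline dose", with a two-hour window after the OIT dose.

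**Definition.** Section 6.1 states: "Any symptoms requiring treatment for anaphylaxis (adrenaline, steroids, salbutamol) following an OIT dose will be classified as a SERIOUS ADVERSE REACTION".

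**Continuation.** Section 5.3.4.3 covers reactions within two hours of an OIT dose, in hospital or at home. Its first rule begins "For a single reaction consisting of wheeze, persistent cough, difficulty breathing, stridor or marked swallowing difficulties". It then says that "the family must not give further OIT doses without contacting the research team", and continues: "The previous lower dose will be given the next possible day, ideally under medical observation on the Research Unit".

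**Emergency treatment.** Section 5.2.4 says "Symptoms of anaphylaxis will be treated initially with IM adrenaline". The signs of anaphylaxis in Figure 6 include "wheeze or persistent cough", and any one listed sign triggers adrenaline. Section 5.3.4 gives this plan to active-group families for home dosing.

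**Follow-up and analysis.** For children withdrawn from active treatment, sections 4.3 and 7.2 name only quality-of-life follow-up. Section 5.4 invites every subject in both arms to the 12-month DBPCFC. Section 7.2 analyses every child in the allocated arm, whether or not the regimen was completed.

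**The concern.** Sections 4.3 and 5.3.4.3 are both written as mandatory, and for the same treated reaction they end in opposite places: the child leaves the study, or the child takes peanut again at a lower dose. Whether a child continues an allergen after a reaction treated with adrenaline is a safety matter, and a protocol should not answer it in two ways.

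There is also a consequence for the trial. During the first 12 months only active-arm children take OIT, so the reading that the team adopts changes who stays on treatment in one arm only. The plan does not say clearly whether a child withdrawn for a reaction still supplies the 12-month DBPCFC, or how a missing one is counted. The choice of reading could therefore reach the primary endpoint.

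**Working it through.** No arithmetic applies. The check follows one case through the text: an active-arm child has wheeze and difficulty breathing within two hours of an OIT dose, receives one IM adrenaline dose and needs no second.

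1. **Are the signs in 5.3.4.3 anaphylaxis under Figure 6?** Largely yes.

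| Sign in 5.3.4.3 | Figure 6 |
|---|---|
| Wheeze | Listed |
| Persistent cough | Listed |
| Difficulty breathing | Listed, as difficult breathing |
| Stridor | Not named; noisy breathing is the nearest entry |
| Marked swallowing difficulties | Listed, without the qualifier |

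2. **Treatment.** One sign is enough for adrenaline, both on the unit (5.2.4) and at home (5.3.4).

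3. **Classification.** The reaction followed an OIT dose and required adrenaline. Under 6.1 it is a serious adverse reaction. The number of adrenaline doses plays no part in that definition.

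4. **Section 4.3.** The item has two limbs joined by and/or, so either suffices. Limb 1 (a serious adverse reaction) is met. Limb 2 (more than one adrenaline dose) is not. Result: withdrawal from the study.

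5. **Section 5.3.4.3.** The first rule is met. It makes no exception for reactions treated with adrenaline. Result: OIT continues at the preceding lower dose.

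6. **Precedence.** Neither section refers to the other. Section 8.2 lets the clinician depart from protocol treatment if the reason is recorded, but does not rank the rules. Section 5.9.1 lets the IDMC request a participant's withdrawal, but sets no rule for this case.

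7. **Test of alignment.** Anaphylaxis that needs two or more adrenaline doses within two hours of an OIT dose is a subset of reactions that require treatment for anaphylaxis after an OIT dose. Under 6.1, every case in limb 2 is already in limb 1, so limb 2 adds nothing. This suggests that the two sections were not written against one definition.

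8. **After withdrawal.** Section 4.3 uses withdrawal from active treatment (child remains for quality of life) and withdrawal from the study (the listed events) side by side without separating them. Section 5.8.2 and Appendix 3 add only quality-of-life and interview contact at 1 and 6 months. Section 5.4 and the ITT statement in 7.2 point the other way, towards a 12-month result for everyone. No passage says how an absent result counts.

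**The case against.** **Withdrawal comes first.** On this reading 4.3 decides who remains on OIT, and 5.3.4.3 governs dosing only for those who remain. The reading is coherent and may be what was meant, and the contact step could be where the team applies it. But 5.3.4.3 does not say so, and its first rule would then have few cases left, because most of its signs call for adrenaline.

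**A narrower serious adverse reaction in 4.3.** The separate limb for more than one adrenaline dose suggests that 4.3 had a more severe event in mind. So does its rule that home anaphylaxis not given adrenaline leads to suspended updosing and retraining. It might be added that 6.1 is a reporting definition. This is the best defence, but 4.3 uses the 6.1 term without qualification and 6.1 is the only place that defines it for OIT doses.

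**Families are protected.** This stands. A reader might infer that families hold two conflicting instructions, or that four sections compete. The documents do not support either. Emergency treatment is the same under both rules, families must speak to the team before another dose, and active-group families have round-the-clock access to a senior doctor. Only 4.3 and 5.3.4.3 give competing actions; Figure 6 and 6.1 are the links between them.

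**The primary outcome is already covered.** This stands in part. Section 5.4 invites all subjects, the ITT statement is broad, 8.2 keeps children given alternative treatment in follow-up and analysis, and 7.1 allows for 20% loss. What is missing is agreement between these and the quality-of-life-only wording, and a rule for counting a missing challenge.

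**Conclusion.** The contradiction is real and should be corrected. Section 4.3 read with 6.1 requires withdrawal after an OIT reaction that needed even one adrenaline dose. Section 5.3.4.3 continues OIT after a reaction with largely the same signs, and no passage ranks them. The conflict falls on the study team's decision after the family has made contact.

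The conclusion rests on 4.3 using the term serious adverse reaction as 6.1 defines it. If 4.3 means something narrower, the remedy is to say so.

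The effect on the primary endpoint cannot be derived. A reader might infer that the ambiguity could cost the trial its significant result. The documents do not support that: they give no rate of treated reactions, no rule that counts withdrawn children as failures, and no ground for assuming that such children would otherwise have passed. For scale only, with 30 active children planned in 7.1, one child is 1/30 = 3.3 percentage points of that arm. How many children would be affected is unknown.

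**What to change.** 1. The clinical team reconciles 4.3, 5.3.4.3 and 6.1, with 5.2.4 and Figure 6, so that each type of reaction leads to one stated action. Section 4.3 states whether it uses the 6.1 definition. No view is offered here on which clinical rule is right.
2. Use separate terms for *stopped OIT* and *left the study*. Reconcile the quality-of-life-only wording in 4.3 and 7.2 with the 12-month invitation in 5.4 and the ITT statement in 7.2.
3. As a secondary point, state in 7.2, before the data are seen, how a missing 12-month DBPCFC counts in the ITT primary analysis.

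The cost is a wording amendment and one sentence in 7.2. No patients, visits or procedures are added.

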5 STUDY PROCEDURES

The main study procedures are shown in Figure 2, and consist of the following stages:

- 1. Recruitment and initial screening
- 2. Initial double-blind, placebo-controlled food challenge (DBPCFC) to roasted peanut.
- 3. **Randomisation and WP1:** Following demonstration of tolerance to one boiled peanut, peanut-allergic children will be randomized 2:1 to either active treatment (OIT using boiled PN) or control (current best practice) during months 0-12.
- 4. **1 year assessment:** All subjects will undergo a DBPCFC to roasted PN, to assess for ongoing clinical reactivity (and determine threshold of reactivity) to roasted PN. Subjects in the active group (Group A) will stop all peanut for 4 weeks and then undergo a further open challenge to assess for tolerance (i.e. sustained unresponsiveness without the ongoing peanut exposure).
- 5. **WP2:** Children in the control group (Group B) will be offered OIT using boiled PN during months 12-24. Subjects in the active intervention groups will be offered ongoing maintenance therapy within the study protocol.
- 6. 2 year assessment and option to determine longer-term tolerance to peanut.

[figure not shown]

Figure 2: Study flowchart and interventions

5.1 RECRUITMENT AND SCREENING VISITS

Peanut-allergic children will be recruited through our clinical service at St Mary's Hospital (Imperial College Healthcare NHS Trust), one of the largest tertiary services in Europe providing specialist paediatric allergy services to the North Thames Region. We will also recruit through our local paediatric allergy network in North West London, including the use of PIC sites at the larger allergy centres. This study requires frequent visits (once every 2-4 weeks) to the Research Unit, thus it is important that participants live relatively local to the unit to minimize travel time and impact on other daily activities.

Potential participants will receive the Study Information either in person, by post or via email, following which the participants will be screened by telephone conversation with their parents, to determine likelihood of true peanut allergy and thus suitability for this study. Suitable participants will then have an appointment made for a screening visit.

The following will take place at the first screening visit:

- Informed consent
- Clinical history and physical examination
- Skin prick test (SPT) to commercial crude peanut extract and boiled peanut slurry according to national guidelines
- For children with asthma, current asthma status will be assessed by the clinician, with the help of lung function testing and completion of a validated asthma control test
- For children with eczema, eczema will be assessed using the SCORAD system¹¹ (which provides an objective measure of eczema severity) as well as completion of a POEM questionnaire, a validated patient-based symptom measure questionnaire

The first screening visit may take place on the same day as the first baseline food challenge, if requested by the family.

5.2 DOUBLE-BLIND, PLACEBO-CONTROLLED FOOD CHALLENGE (DBPCFC) TO ROASTED PEANUT

All participants who fulfil eligibility criteria for the study will undergo a baseline DBPCFC to roasted peanut at enrolment. The DBPCFC is established as the gold-standard test of diagnosis of food allergy by international consensus. The objectives are:

- i. to confirm the diagnosis of IgE-mediated peanut allergy,
- ii. to determine the threshold of clinical reactivity to peanut prior to OIT

The DBPCFC involves 2 half-day visits, at least one week apart. Participants are given incremental doses of peanut or placebo 30 minutes apart, and monitored for signs/symptoms of allergic reaction throughout. The challenge is halted once pre-determined stopping criteria have been reached. DBPCFC will be performed according to the international PRACTALL consensus for best practice.¹²

5.2.1 CLINICAL ASSESSMENT AND CHECKS PRIOR TO DBPCFC

All subjects will be assessed prior DBPCFC to determine suitability for a challenge, as follows:

- No intercurrent illness (viral or otherwise)
- No exacerbation in allergic symptoms (eczema, asthma, food allergy) in the preceding week.
- No short-acting β2 agonists used in the past 12 hours
- No short-acting antihistamine taken (e.g. cetirizine, loratadine) in the past 48 hours (72 hours for fexofenadine)
- No long-acting antihistamine (e.g. chlorphenamine, desloratadine) in the previous 5 days.
- No oral steroids have been taken in the past 2 weeks

¹¹Kunz, B., Oranje, A.P., Labreze, L., Stalder, J.F., Ring, J., and Taieb, A. Clinical validation and guidelines for the SCORAD index: consensus report of the European Task Force on Atopic Dermatitis. Dermatology. 1997; 195: 10–19

¹²Sampson HA, Gerth van Wijk R, Bindslev-Jensen C, et al. Standardizing double-blind, placebo-controlled oral food challenges: AAAAI-EAACI PRACTALL consensus report. J Allergy Clin Immunol. 2012;130:1260-74.

- Baseline observations (temperature, blood pressure, heart and respiratory rate, oxygen saturation) within normal range.
- Baseline physical examination must not reveal any significant acute findings.

Challenges will occur on a Paediatric Allergy Research Unit (PRU) where food challenges are performed on a regular basis, and staff are familiar with the management of allergic reactions including anaphylaxis through clinical experience and regular training. Emergency equipment (including oxygen and suction) and medication will be checked beforehand, as per local protocol and international criteria for performance of DBPCFC.

5.2.2 DBPCFC

The challenge will consist of seven consecutive increasing doses of roasted peanut (or placebo) at 30 minutes intervals with an observation period of 2 hours after the final dose:

Protocol 1: DBPCFC to peanut	Roasted peanut OFC (using defatted flour)			
TIME POINT (mins)	Peanut flour (mg)	Peanut protein (mg)		
0	6	3		
30	20	10		
60	60	30		
90	200	100		
120	600	300		
150	2000	1000		
180	6000	3000		
Cumulative dose 4443mg				
2 hours observation period following last dose to monitor for signs of reaction				

The food challenge doses will be prepared prior to challenge, in a matrix containing soya (soya-allergic children will be given a matrix based on sunflower seed instead). Tolerance to at least one of these will be established at enrolment. All doses (irrespective of active or placebo) will be double-checked prior to administration. The order of challenge days (active or placebo control) will be randomized by an independent research associate, according to a computergenerated randomization list (www.sealedenvelope.com). The randomization key will be recorded in a separate file and logged once both pair of challenges have taken place.

In brief, symptoms will be monitored during the challenge, with detailed assessment prior to each challenge dose, according to Figure 3.

- Green symptoms: Not generally sufficient to consider a challenge positive unless symptoms persist for at least 120 minutes.
- Orange symptoms: Symptoms that recur on 3 doses, or persist (e.g. 40 minutes) are more likely indicative of a reaction than when such symptoms are transient and not reproducible. 3 or more scoring areas in orange more likely represent a true response, and if present the challenge should be halted.
- Red symptoms: A single red symptom is likely to indicate a true response, and if present the challenge should be halted.

The outcome of the challenge (positive or negative) and the apparent eliciting threshold dose will be recorded in the participant record.

Challenge outcome will be determined as per the PRACTALL Consensus criteria,⁹ as shown in Figure 3:

```
I. SKIN
        A. Pruritus
              0 = Absent
              1 = Occasional scratching
              2 = Scratching continuously for >2 minutes at a time
              3 = Hard continuous scratching causing excoriations
        B. Urticaria/Angioedema
              0 = Absent
              1 = < 3 hives, or mild lip oedema
              2 = < 10 hives but >3, or significant lip, tongue or facial oedema
              3 = Generalized involvement
        C. Rash
              0 = Absent
              1 = Few areas of faint erythema
              2 = Areas of erythema
              3 = Generalized marked erythema (>50%)
II. UPPER RESPIRATORY
        A. Sneezing/Itching
              0 = Absent
              1 = Rare bursts, occasional sniffing
              2 = Bursts <10, intermittent rubbing of nose/eyes or frequent sniffing
              3 = Continuous nasal/eye itch, periocular swelling and/or long bursts of
                  sneezing, persistent rhinorrhoea
III. LOWER RESPIRATORY
        A. Wheezing
              0= Absent
              1 = Expiratory wheeze on auscultation
              2 = Biphasic wheeze
              3 = Use of accessory muscles, audible wheezing
        B. Laryngeal
             0= Absent
              1 = >3 discrete episodes of throat clearing/cough, or persistent throat
                 tightness/pain
              2 = Vocal hoarseness, frequent cough
              3 = Stridor
IV. GASTROINTESTINAL
        A. Subjective Complaints
              0 = Absent
              1 = Complaints of nausea or abdominal pain, itchy mouth/throat
              2 = Frequent c/o nausea or pain with normal activity
              3 = Notably distressed due to GI symptoms with decreased activity
        B. Objective Complaints
              0 = Absent
              1 = 1 episode of emesis
              2 = 2-3 episodes of emesis or diarrhoea or 1 of each
              3 = >3 episodes of emesis or diarrhoea or 2 of each
V. CARDIOVASCULAR/NEUROLOGIC
              0 = normal heart rate or BP for age/baseline
              1 = Subjective symptoms (weak, dizzy), or tachycardia
              2 = Drop in mBP of >20% from baseline, or significant change in mental status.
              3 = Cardiovascular collapse, signs of impaired circulation (unconscious)
```

Figure 3: PRACTALL consensus stopping criteria for food challenges.⁹

For safety reasons, families will be asked to provide their child with a snack one hour after the challenge has ceased i.e. prior to leaving the research unit. This is to avoid the possibility of further symptoms on feeding outside the medical unit, something which can occur if no food is eaten prior to discharge.

All families will be contacted by email or telephone the day following challenge to collect any data relating to the occurrence of delayed (late phase) symptoms.

